APPENDIX A: CASE REPORT FORM (CRF)

GECKO Case Report Form (CRF)

Use with Appendix B (Data Dictionary) to help data collection.

REDCap unique ID	
Data collection period	

Section 1: Pre-operative data fields								
Age	Sex	M  F 	ASA	I  II  III  IV  V 	BMI	--	Frailty	1  2  3  4  5  6  7  8  9 
Comorbidities (Tick all that apply)	 MI  CHF  PVD  CVA/TIA  Dementia  COPD  CTD  PUD  Hemiplegia  Leukaemia  Lymphoma  HIV/AIDS  Hypertension  IBD		 Diabetes mellitus  Diet-controlled  Non-insulin  Insulin controlled		 Solid tumour  Localised  Metastatic		History of acute cholecystitis or cholangitis	 Yes  No
	 Liver disease  Mild  Moderate to Severe		 CKD  I  II  IIIa  IIIb  IV  V		 None of the Above			
	USS:  Yes  No - not available  No - not indicated  No - patient declined  Unknown CT:  Yes  No: not available  No: not indicated  No: patient declined  Unknown MRCP:  Yes  No: not available  No: not indicated  No: patient declined  Unknown ERCP:  Yes  No: not available  No: not indicated  No: patient declined  Unknown EUS:  Yes  No: not available  No: not indicated  No: patient declined  Unknown HIDA:  Yes  No: not available  No: not indicated  No: patient declined  Unknown							
	Preoperative imaging (Tick all that apply)	 Gallstones  Thick-walled gallbladder  Pericholecystic fluid  CBD stones  Dilated CBD (Diameter: -- . -- mm (1dp))						
Imaging findings	First symptom onset and admission: -- -- Diagnosis and decision to operate: -- -- Decision to operate and surgery: -- --		Urgency of surgery  Elective  Delayed  Emergency (patient was on elective waiting list?)  Yes  No					
Days between	 Acute calculous cholecystitis (Tokyo grade:  I  II  III; Was Tokyo grade documented in notes:  Yes  No)  Biliary colic  Acalculous cholecystitis  Chronic cholecystitis  CBD stone  Polyp  Dyskinesia  Gallstone pancreatitis (Atlanta criteria:  Mild  Mod  Severe; Was Atlanta criteria documented in notes:  Yes  No)							
Indication for surgery	Indication for surgery							
Section 2: Intraoperative data fields								
Mode of anaesthesia (Tick all that apply)	 Local (Route:  Subcutaneous  Intraperitoneal)  Regional (Route:  spine-related  regional nerve block)  Sedation		 General inhaled (Type:  sevoflurane  halothane  desflurane  N2O  isoflurane)  Total Intravenous Volatile Anaesthetic		Intraoperative antibiotics  Yes - Prophylactic  Yes - Intra-op spillage  Yes - cholecystitis  No			
Primary operator	 Consultant or attending (Specialty:  General  OG  HPB  Colorectal  Breast  Vascular  Other:)  Surgical trainee (Grade:  Senior  Junior; Training operation?  Yes  No; Consultant present?  Yes  No)  Non-surgeon Number of cholecystectomies performed by primary surgeon prior to this procedure:  0-50  51-100  101-200  >200							
Operative approach	 Open (Why?  No laparoscopy  Surgeon not trained in laparoscopy  Laparoscopy broken  Previous surgeries  Disease severity)  Open conversion (Why?  Suboptimal view  Adhesions  Unable to safely dissect CVS  Suspected BDI  Pneumoperitoneum not tolerated  Bleeding  Bowel injury  Equipment failure  Suspected or actual cholecystoduodenal or cholecystocolonic fistula  Laparoscopic (Type:  Standard  SILS; Gasless?  Yes  No; Reusable equipment:  Yes  No)  Robotic (Type:  Standard  SILS; Gasless?  Yes  No; Reusable equipment:  Yes  No)							
Intraoperative difficulty (Nassar) - for minimally invasive technique	 I  II  III  IV  V	CVS obtained successfully? - for minimally invasive technique  Yes  No		If No, which criteria was met? (Tick all that apply)  Clearance of the hepatocystic triangle  Exposure of the lower cystic plate  Only two structures are attached to the gallbladder  None of the above		Was there a time-out to verify CVS?  Yes  No		
Operation performed	 Total cholecystectomy (Type:  Standard  Fundus-first approach)  Subtotal cholecystectomy (Type:  Reconstituting  Fenestrated)  Not performed ( Diagnostic laparoscopy  Cholecystostomy)		Abdominal drain  Yes  No		Anatomical biliary variant  Yes  No			
Intraoperative CBD assessment (Tick all that apply)	 Intraoperative cholangiogram  Incisionless fluorescent cholangiography  Laparoscopic US  Intraoperative ERCP Decision:  Selective  Routine; If selective, indication:  Raised LFT  BDI concern  Pre-op imaging suggests CBD stone Findings:  Stone  No stone; If stone, management:  Flushing with saline and smooth muscle relaxant  Fogarty catheter trawl  Basket retrieval  Choledochoscope  No intraoperative treatment attempted							
CBD exploration	 Yes (Type:  Trancystic  Choledochotomy; If Choledochotomy, closure:  Primary closure  T-tube)  No		Operative contamination  Clean  Clean-Contaminated  Contaminated  Dirty					
Intraoperative complications - excluding BDI (see section 4)	 Bile spill  Stones Spilt  Bleeding  Major vascular injury  Bowel injury		Reusable gowns  Yes ( All staff  some staff)  No		Reusable drapes  Yes  No			
Section 3: 30-day outcomes								
Highest 30-day Clavien-Dindo (CD)	 0  I  II  IIIa (Radiological drainage?  Yes  No)  IIIb (Re-operation?  Yes  No)  IVa  IVb  V (Postop day of death: --)		Unplanned critical care admission  Yes (Length of stay: --)  No		Unplanned Re-imaging  Yes  No		 Yes  No	
30-day postoperative Complications (Tick all that apply)	 Surgical site infection (CD Grade:  I  II  IIIa  IIIb  IVa  IVb  V)  Pulmonary complications (CD Grade:  I  II  IIIa  IIIb  IVa  IVb  V)  Bile leak (CD Grade:  I  II  IIIa  IIIb  IVa  IVb  V)  Bleeding (CD Grade:  I  II  IIIa  IIIb  IVa  IVb  V)  Intra-abdominal collection (CD Grade:  I  II  IIIa  IIIb  IVa  IVb  V)  Acute pancreatitis (CD Grade:  I  II  IIIa  IIIb  IVa  IVb  V)							
Length of stay	-- days		Unplanned 30-day Readmission  Yes (Length of stay: --)  No					

Section 4: BDI data fields			
BDI identified at 30-day follow-up of index cholecystectomy	 Yes (if yes, please fill in the rest of the data points below)  No (Was BDI identified at one-year of index cholecystectomy:  Yes  No (if yes, please fill in the rest of the data points below))		
Presentation of BDI	 Intraoperatively  Controlled bile leak from abdominal drain  Abdominal pain due to uncontrolled bile leak  Obstructive jaundice or cholangitis  Intra-abdominal abscess or biloma		Days from index cholecystectomy to diagnosis (0 = intraoperatively) --
BDI grade (Strasberg)	 A  B  C  D  E1  E2  E3  E4  E5	Concomitant vascular injury  Yes  Right hepatic artery  Common hepatic artery  Main portal vein  Right portal vein  No	
Imaging modality to investigate and confirm BDI	 OTC  USS  MRCP  CT  ERCP  PTC  Nuclear medicine scan  Tubogram  None	Discussion with specialist HPB centre  Yes  No  Not required - Injury occurred at specialist HPB centre	(Days from injury to referral: __ ; Transferred?  Yes  No)
Management of BDI (Tick all that apply)	 ERCP alone (Days after index cholecystectomy: __)  ERCP and stent (Days after index cholecystectomy: __)  PTC (Days after index cholecystectomy: __)  Washout only (Days after index cholecystectomy: __)  Surgical repair (Days after index cholecystectomy: __)		
Specialty of surgeon performing BDI repair	 HPB surgeon  UGI surgeon  General surgeon	Method of repair  Roux-en-Y Hepaticojejunostomy  CBD repair without T-tube  CBD repair with T-tube  CBD end to end anastomosis  Hepaticoduodenostomy	Vascular repair  Yes  No
One-year complications (Tick all that apply)	 Stricture formation (Days from repair to complication: __)  Cholangitis (Days from repair to complication: __)  Anastomotic leakage (Days from repair to complication: __)  Intra-abdominal abscess or biloma (Days from repair to complication: __)  Re-repair (Days from repair to complication: __)		If BDI surgical repair
Section 5: Histology data fields			
Postoperative histology	 Not sent for examination  Sent for examination (Indication:  Routine  Selective; Days from index cholecystectomy to histology result: __ ; Result:  Benign  Malignant (if malignant, please fill in the rest of the data points below))		
Staging investigations after index cholecystectomy	 CT thorax abdomen pelvis (Days from histology result to staging: __)  MRI liver (Days from histology result to staging: __)  PET-CT (Days from histology result to staging: __)  Staging laparoscopy (Days from histology result to staging: __)		
TNM grade (AJCC 8th edition)	T category:  Tis  T1a (lamina propria)  T1b (muscularis)  T2a (peritoneal side)  T2b (hepatic side)  T3  T4 N category:  N0  N1 (1-3 nodes)  N2 (>3 nodes) M category:  M0  M1		
Discussed at MDT	 Yes  No	Adjuvant treatment  Chemotherapy  Radiotherapy  None	
Revisional surgery	 Yes  No - not required  No - unresectable tumour		
Type of revisional surgery (Tick all that apply)	 Liver resection (Extent:  Liver bed  1 segment  2 segments  ≥ 3 segments)  Bile duct resection  Lymph node dissection	Days from histology result to revisional surgery --	If revisional surgery
Pathology results	Resection margin status:  R0  R1  R2 Lymphovascular invasion:  Yes  No Perineural invasion:  Yes  No		
Recurrence on imaging at one year	 Yes (Days from surgery to recurrence: __)  No		
Section 6: One-year outcomes			
Highest one-year Clavien-Dindo (CD)	 0  I  II  IIIa (Radiological drainage?  Yes  No)  IIIb (Re-operation?  Yes  No)  IVa  IVb  V (Postop day of death: __)	Total number of readmissions --	
One-year complications (Tick all that apply)	 Surgical site infection (CD Grade:  I  II  IIIa  IIIb  IVa  IVb  V)  Pulmonary complications (CD Grade:  I  II  IIIa  IIIb  IVa  IVb  V)  Bile leak (CD Grade:  I  II  IIIa  IIIb  IVa  IVb  V)  Biliary stricture (CD Grade:  I  II  IIIa  IIIb  IVa  IVb  V)  Bleeding (CD Grade:  I  II  IIIa  IIIb  IVa  IVb  V)  Intra-abdominal collection (CD Grade:  I  II  IIIa  IIIb  IVa  IVb  V)  Acute pancreatitis (CD Grade:  I  II  IIIa  IIIb  IVa  IVb  V)		

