4. **Antibiotic use:** Antibiotics are not required in low risk patients undergoing laparoscopic cholecystectomy, but may reduce the incidence of wound infection in high risk patients (age > 60 years, the presence of diabetes, acute colic within 30 days of operation, jaundice, acute cholecystitis, or cholangitis) [12].
5. **Use of drains:** drains are not needed after elective laparoscopic cholecystectomy and their use may increase complication rates; however, they may be useful in complicated cases particularly if choledochotomy is performed [12].
6. **Bile Duct Injury (BDI):**
 - a. If major BDI occur, outcomes are improved by early recognition and immediate referral to experienced hepatobiliary specialists for further treatment before any repair is attempted by the primary surgeon, unless the primary surgeon has significant experience in biliary reconstruction [7,8,12].
 - b. If considering all types of BDIs, rates are 0.4% and 0.8% for elective and emergency settings, respectively [7].
 - c. It is recommend knowing Strasberg's classification, which remains the most commonly used classification for BDIs [7].

Post-operative

1. **30-day readmission:** rate should be <10% [11].
2. **Critical care:** There should be access to critical care beds (both level 2 and level 3) with on-site renal support [11].

OVERVIEW OF STUDY DESIGN

GECKO is a prospective, international, multicentre, observational cohort study delivered by GlobalSurg Collaborative. This will be on consecutive patients undergoing cholecystectomy, between 31st July 2023 to 19th November 2023, with follow-up at 30-day and one-year postoperatively. Mini-teams of up to five collaborators ([see page 17](#)) per 14-day data collection period will prospectively collect data at each participating centre.

GLOBALSURG COLLABORATIVE

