2. Intraoperative antibiotics*	
Yes (Prophylactic / Intraoperative spillage / Cholecystitis) / No *Defined as administration of antibiotics at least 30 minutes prior to skin incision to end of operation

3. Primary operator	
Consultant or attending Senior trainee (i.e., senior registrar or resident with >4 years surgical training/residency) Junior trainee (i.e., junior registrar or resident with ≤ 4 years surgical training/residency) Non-surgeon (e.g., medical practitioner or nurse)
 
If Consultant: What specialty? (General / Oesophago-gastric (OG) / HPB / Colorectal / Breast / Vascular / Other) If Trainee: Was this a training operation? (Yes / No). Was a consultant present? (Yes / No) If any: Number of cholecystectomies performed prior to this procedure: 0-50 / 51-100 / 101-200 / >200

4. Operative approach	
Open / Open conversion / Laparoscopic (Standard / Single Incision Laparoscopic Surgery (SILS)) / Robotic (Standard / SILS)
 
 If open, why: No laparoscopic equipment / Surgeon not trained in laparoscopy / Laparoscopy equipment broken / Multiple previous surgery / Disease severity. If open conversion, why: Suboptimal view / Adhesions / Not able to safely dissect CVS / Suspected bile duct injury / Patient unable to tolerate pneumoperitoneum / Bleeding / Bowel injury / Laparoscopic or robotic equipment failure / Suspected or actual cholecystoduodenal or cholecystocolonic fistula. If laparoscopic or robotic: was this gasless (Yes / No), were reusable equipment used? (Yes / No).
5. Intra-operative difficulty score – this is for minimally invasive surgery	
I / II / III / IV / V (Nassar Grade: Appendix D for definitions)

6. Was the Critical View of Safety (CVS) obtained (all three) – this is for minimally invasive surgery	
Yes / No If no, which criteria was met: 1) Clearing fat and fibrous tissue from the hepatocystic triangle.

	2) The lower third of the gallbladder being cleared from the cystic plate. 3) Only two structures are attached to the gallbladder.
7. Was there a time-out to verify CVS	Yes / No Defined as a momentary pause that what one is seeing is likely the correct anatomy

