
6. Imaging modality to investigate and confirm BDI
	
On-table cholangiography (OTC) / USS / MRCP / CT / ERCP / Percutaneous transhepatic cholangiography (PTC) / Nuclear medicine scan (e.g. Functional liver scan) / Tubogram / None

7. Discussion with a specialist HPB centre
	
Yes / No / Not required (Injury occurred at specialist HPB centre) If yes:
 
 Transferred to specialist HPB centre: Yes / No Time from injury to referral: number of days (whole number)

8. Management of Bile duct injury (Select all that apply)
	
Non-surgery (ERCP only / ERCP and stent / PTC) / Surgery (washout only / repair) If any of the above:
 
 Time after index cholecystectomy: number of days (Whole number, day of index cholecystectomy = day 0) 
If surgical repair:
 
 Specialty of surgeon performing Bile duct injury repair: HPB surgeon / UGI surgeon / General surgeon Method of repair: Roux-en-Y Hepaticojejunostomy / CBD repair without T-tube / CBD repair with T-tube / CBD end to end anastomosis / Hepaticoduodenostomy Vascular repair: Yes / No One-year complications: Stricture formation / Cholangitis / anastomotic leakage / intra-abdominal abscess or biloma / re-repair. If yes to any, time from repair to complication: number of days (Whole number, day of repair = day 0)

	Stricture definition: defined as a clinically relevant stricture leading to either jaundice, significant alterations of the liver function tests, cirrhosis or reoccurring cholangitis requiring radiological/surgical intervention or a liver failure related death
Histology data fields	Required data (definition / comment)
1. Postoperative histology	
Not sent for examination / Sent for examination
 
If sent for examination, please complete:
 
 • Indication: Routine / Selective • Time from index cholecystectomy to histology result: Number of days (whole number) • Result: Benign / Malignant 
If Malignant, please complete the rest of the data points below

2. Staging investigations after index cholecystectomy (select all that apply)	
CT thorax abdomen pelvis / MRI liver / PET-CT / Staging laparoscopy
 
For any of the above, please indicate time from histology result to staging investigation: number of days (whole number)

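### The bile duct injury form waives specialist discussion by hospital, audit standard 6a by the primary surgeon's experience, so compliance with 6a can be misclassified in either direction and only partly corrected

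*Protocol*

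**What the plan says.** In the Protocol's Audit Standards (Intra-operative, item 6a), the scope and the action are: "If major BDI occur, outcomes are improved by early recognition and immediate referral to experienced hepatobiliary specialists for further treatment". The timing and the only exception follow: "before any repair is attempted by the primary surgeon, unless the primary surgeon has significant experience in biliary reconstruction". The exception belongs to a person and to a specific skill.

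Section 4 of the case report form (Appendix A) has a field on discussion with a specialist HPB centre. Besides Yes and No, its only option is "Not required - Injury occurred at specialist HPB centre". Appendix B, bile duct injury item 7, repeats it: "Yes / No / Not required (Injury occurred at specialist HPB centre". That exemption belongs to a place. Appendix B asks for the days to referral, and for transfer, only if the answer is Yes.

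Statistical Considerations makes compliance with the audit standards the primary endpoint, and 6a is one of them. The protocol gives no rule that turns the discussion field into compliance with 6a.

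**The concern.** The standard and the form draw the exemption along different lines. Where the two lines agree (an experienced surgeon at an HPB centre, an inexperienced one elsewhere), the field serves. Where they disagree, the recorded code points the wrong way for 6a.

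This is a problem of data capture. An analysis plan can decide how to combine fields, but it cannot derive a fact that no field holds. At stake is whether one component of the primary endpoint can be measured as the protocol words it. The disagreement also depends on hospital type, and the study's aim is to compare settings.

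**Working it through.** **Step 1. Standard against code, for a repair by the primary surgeon with no outside discussion.**

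| Where the injury occurred | Primary surgeon experienced in reconstruction | HPB specialist involved | By 6a | Code on the form |
|---|---|---|---|---|
| HPB centre | Yes | No | Exempt | Not required (agrees) |
| HPB centre | No | No | Not met | Not required (**wrongly waived**) |
| Elsewhere | Yes | No | Exempt | No (**wrongly adverse**) |
| Elsewhere | No | No | Not met | No (agrees) |

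**Step 2. Can other fields repair rows 2 and 3?**

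- Operator specialty, asked of consultants only: "What specialty? (General / Oesophago-gastric (OG) / HPB / Colorectal / Breast / Vascular / Other". It flags an HPB consultant operating elsewhere (part of row 3). Trainees have no specialty recorded, and specialty is not the same as reconstruction experience.
- Operator experience: "Number of cholecystectomies performed prior to this procedure: 0-50 / 51-100 / 101-200 / >200". This counts cholecystectomies, not reconstructions.
- Specialty of the repairing surgeon (HPB, UGI or general), asked if there was a surgical repair. A general surgeon repairing at an HPB centre becomes visible (part of row 2). The field does not say whether this was the primary surgeon.
- Trainee grade, consultant presence, days to repair and Strasberg grade give context. The site survey records whether the hospital has an HPB team, not whether that team was involved in the case.

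Three facts remain unrecorded: experience in biliary reconstruction, in-house specialist referral at an HPB centre, and whether the primary surgeon did the repair.

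**Step 3. Number of cases.** Inputs: about 15,000 patients (Data Analysis & Sample Size); BDI of all types 0.4% elective and 0.8% emergency (Audit Standards, item 6b).

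- 15,000 × 0.004 = 60; 15,000 × 0.008 = 120.
- One misclassified case moves a compliance rate by 100/60 = 1.7 or 100/120 = 0.8 percentage points if every BDI is in the denominator. It moves the rate by more if only major injuries count; the protocol does not give their share.

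**Step 4. Net error, as an illustration.** None of these inputs is in the documents. Let h be the share of injuries at HPB centres, f the share of those wrongly waived, and e the share of the rest wrongly coded No. Suppose 6a were scored from this field alone, with the not-required code counted as compliant. Then the net error in points is 100 × [h·f − (1 − h)·e].

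| h | f | e | Net error (points) |
|---|---|---|---|
| 0.3 | 0.1 | 0.05 | 3.0 − 3.5 = −0.5 |
| 0.3 | 0.1 | 0.20 | 3.0 − 14.0 = −11 |
| 0.6 | 0.3 | 0.05 | 18.0 − 2.0 = +16 |
| 0.6 | 0.3 | 0.20 | 18.0 − 8.0 = +10 |

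The sign changes with the inputs. In the pooled rate the two errors partly cancel.

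**The case against.** **No scoring rule.** Nothing in the protocol says that 6a is read from this field, or that the not-required code counts as compliant. Combining fields into compliance is normally left to the analysis plan. This stands. It limits the point to what can go wrong and what cannot be recovered.

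**Purpose of the field.** Its label and the transfer question beside it describe contact between hospitals. A centre does not refer to itself, so the option may be an ordinary not-applicable code that serves the secondary aim on adverse events and their management. That is a fair reading and a reason to keep the code. It leaves 6a without a field that captures its own exception.

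**Other fields help.** They do, as step 2 shows, and the repairing surgeon's specialty helps most. Recovery stays incomplete.

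**Few cases.** Only major injuries repaired by the primary surgeon, with surgeon experience and hospital type discordant, are affected; that may be a handful. The protocol also says that attaining some standards will not be a definitive measure of quality. Both points bear on priority and do not remove the mismatch.

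**Stronger readings.** A reader might infer that HPB centres can never fail 6a, or that the error favours settings with more such centres. The first needs the scoring rule that the protocol does not state. The second needs the distribution of HPB centres over human development index (HDI) groups and the net direction of error, and neither is given. One can build an example in which the ranking of hospital types reverses. Take 30 major injuries, 12 at HPB centres: by the standard 7/12 = 58% there and 15/18 = 83% elsewhere; from the code alone 12/12 = 100% and 12/18 = 67%. The reversal comes from the chosen counts, not from anything in the documents.

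**Conclusion.** The concern holds in a limited form. The discussion field does not map onto the exception in 6a. Taken with the other fields, the form still cannot fully establish compliance with 6a as worded, and the error can run either way. It touches one component of the primary endpoint and some part of the major injuries among an expected 60 to 120 of all types, taking the protocol's rates and 15,000 patients at face value. The −11 to +16 points in the working only show that the sign is not determined; they are not an estimate. The documents do not support saying that compliance is misclassified outright, that HPB centres are bound to look better, or that the HDI comparison is biased in a known direction. Because the missing facts cannot be derived later and are cheap to collect, the form should be changed.

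**What to change.** In Section 4 of the case report form and Appendix B, bile duct injury item 7, keep the place code as a descriptive option and add three items for every hospital:

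- (a) HPB specialist involved, in-house or external: Yes/No, with the day.
- (b) Repair done by the primary surgeon: Yes/No.
- (c) Primary surgeon experienced in biliary reconstruction: Yes/No.

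Assess 6a for major injuries from these items and not from hospital type, so that the standard, the form and the dictionary are reconciled. This changes what is recorded and takes no position on how injuries should be managed.

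The cost is three Yes/No answers and one day count per injury, about 3 × 60 = 180 to 3 × 120 = 360 Yes/No answers over the whole study. The downside is that experience is self-declared. Report 6a a second time with operator and repairing-surgeon specialty as the proxy, so that readers can see how far the result depends on the declaration.

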2. Unplanned critical care admission - where critical care admission was not part of pre-operative plan	Yes / No If yes, please indicate length of stay in critical care: number of days (whole number)
3. Unplanned Re-imaging - where imaging in post-operative period (e.g.,	Yes / No If yes then tick all that apply: USS / CT / MRI / ERCP

CT, MRCP) was not part of pre-operative plan
	

4. 30-day postoperative complications (Select all that apply)
	
Surgical site infection (CD Grade* 0 / I / II / IIIa / IIIb / IVa / IVb / V) Postoperative pulmonary complications (CD Grade* 0 / I / II / IIIa / IIIb / IVa / IVb / V) Bile leak (CD Grade* 0 / I / II / IIIa / IIIb / IVa / IVb / V) Bleeding (CD Grade* 0 / I / II / IIIa / IIIb / IVa / IVb / V) Intra-abdominal collection (CD Grade* 0 / I / II / IIIa / IIIb / IVa / IVb / V) Acute pancreatitis (CD Grade* 0 / I / II / IIIa / IIIb / IVa / IVb / V) *For all of the above, please indicate the Clavien-Dindo grade associated with that complication

5. Length of stay
	
Whole number of days (Where discharge < 23 hours, enter 0. If the patient has not been discharged prior to the end of 30-day follow-up, enter '31')

6. Unplanned readmission within 30 days
	
Yes (Length of stay) / No

Bile Duct Injury (BDI) data fields
	
Required data (definition / comment)

1. BDI identified within 30-days of index cholecystectomy
	
Yes / No If yes: please fill in the rest of the data points below. If No: Was BDI identified within one-year of index cholecystectomy: Yes / No (if yes, then please fill in the rest of the data points below)

2. Presentation of BDI
	
Intraoperatively / Controlled bile leak from surgically placed abdominal drain / Abdominal pain due to uncontrolled bile leak / Obstructive jaundice or cholangitis / Intra-abdominal abscess or biloma

3. Days from index cholecystectomy to diagnosis
	
Number of days (0 = intraoperatively)

4. Bile duct injury grade
	
A / B / C / D / E1 / E2 / E3 / E4 / E5 (Strasberg Injury Grade: Appendix D for definition)

5. Concomitant vascular injury
	
Yes (Right hepatic artery / Common hepatic artery / Main portal vein / Right portal vein) / No

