Pulmonary complications [31]	Atelectasis OR pneumonia OR pulmonary aspiration OR acute respiratory distress syndrome
Bile leak	Grade A: bile leak which requires little or no change in the patient's management; resolves with conservative management within 1 week. Grade B: bile leak or collection which requires additional diagnostic or interventional procedures, such as ERCP or re-laparoscopy or Grade A bile leak which lasts more than 1 week. Grade C: Bile leak or collection which requires re-laparotomy.
Intra-abdominal abscess/collection	A clinical diagnosis of intra-abdominal collection (fever or abdominal pain or wound infection with dehiscence of any layer below fat/Scarpa's fascia) with operative or radiological evidence of a collection.
Acute pancreatitis [28]	Diagnosed using the revised Atlanta guidelines which state the diagnosis of acute pancreatitis requires two of the following three features: 
 Abdominal pain consistent with acute pancreatitis (acute onset of a persistent, severe, epigastric pain often radiating to the back) Serum lipase activity (or amylase activity) at least three times greater than the upper limit of normal Characteristic findings of acute pancreatitis on contrast-enhanced computed tomography.
Common bile duct injury [32-34]	Any injury to the main biliary tree will be classified using the Strasberg Classification System (see figure below): A – leak from cystic duct or small duct in liver bed B – occlusion of an aberrant right hepatic duct C – leak from an aberrant right hepatic duct D – lateral injury to the common hepatic or bile duct (<50% of circumference) E1 – transection or stricture of common hepatic or common bile duct >2cm from the hilum. E2 - transection or stricture of common hepatic duct <2cm from the hilum. E3 – Transection of the common hepatic duct at the level of the bifurcation without loss of contact between left and right hepatic duct. E4 – Transection of the common hepatic duct at the level of the bifurcation with loss of communication between the left and right hepatic duct. E5 – injury of a right segmental duct combined with an E3 or E4 injury.

Strasberg Classification System

American Joint Committee on Cancer (AJCC) 8th Edition TNM Stage

Category [35]	Definition
T category	
Tis	Carcinoma in-situ
T1a	Limited to the lamina propria
T1b	Invades the muscle layer
T2a	Invades the perimuscular connective tissue on the peritoneal side

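### The bile duct injury form has no accurate method-of-repair option, and no open category, for surgical closure of a Strasberg A leak or simple closure of an aberrant duct

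*Protocol*

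**What the plan says.** Appendix D opens its injury definition with "Any injury to the main biliary tree will be classified using the Strasberg Classification System" and then lists the grades. The first is "A – leak from cystic duct or small duct in liver bed". Aberrant-duct injuries are grades B (occlusion) and C, the latter worded "C – leak from an aberrant right hepatic duct".

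Appendix B records the grade for every injury as "A / B / C / D / E1 / E2 / E3 / E4 / E5 (Strasberg Injury Grade: Appendix D for definition", and Section 4 of the case report form (Appendix A) has a tick box for each grade.

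Management of any injury, whatever its grade, is then recorded in Appendix B, bile duct injury item 8, as "Non-surgery (ERCP only / ERCP and stent / PTC) / Surgery (washout only / repair". Choosing repair opens "Method of repair: Roux-en-Y Hepaticojejunostomy / CBD repair without T-tube / CBD repair with T-tube / CBD end to end anastomosis / Hepaticoduodenostomy". The case report form carries the same five methods, including "CBD repair without T-tube". Neither place has an open category.

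Surgeon specialty, vascular repair and a set of one-year complications, each timed from the repair, are asked only after surgical repair. Secondary aim 2 is to assess adverse events such as bile duct injury, and how they are managed.

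**The concern.** A response list has to cover every event that the form sends to it. Here the form sends all Strasberg grades to one repair list, and that list is written for reconstruction or repair of the main ducts. A reoperation that sutures or clips a leaking cystic stump is surgical and is more than a washout, yet it matches none of the five methods.

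A data collector facing this case has three ways out, and each damages the record differently:

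- Leaving the method blank loses what was done.
- Ticking washout only undercounts repairs. It also closes the fields for surgeon specialty, re-repair and time from repair.
- Ticking a common bile duct repair reports an operation that did not take place.

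Method of repair is a central variable for describing injury management. An analysis plan cannot recover a category that was never collected.

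**Working it through.** The protocol states no figure for this field, so there is nothing to reproduce. The check is a comparison of response options, followed by the scale.

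**1. Injuries that enter the field against the methods offered**

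| Injury as defined in Appendix D | Surgical act | Accurate option among the five? |
|---|---|---|
| A: cystic duct or small liver-bed duct leak | Closure of the stump or small duct | No |
| B, C: aberrant right duct | Simple ligation or closure | No |
| B, C: aberrant right duct | Reconstruction onto bowel | Arguably yes, hepaticojejunostomy |
| D, E: main duct | Repair or reconstruction | Yes |

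The clear gap is grade A. For B and C it is limited to simple ligation or closure.

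**2. Is it an extraction fault or a slip in one place?** No. The case report form and the data dictionary give the same five methods. An open category is used elsewhere on the same form, for operator specialty, so the format allows one.

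**3. What is lost under washout only?** The fields conditional on repair are lost: surgeon specialty, method, vascular repair, the separate ticks for cholangitis and re-repair, and time from repair to complication. Section 6 of the case report form still asks every patient about one-year bile leak, biliary stricture and intra-abdominal collection, so those outcomes remain.

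**4. Scale.** The audit standards give all-type injury rates of 0.4% (elective) and 0.8% (emergency). The sample size paragraph anticipates about 15,000 patients.

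- 15,000 × 0.004 = 60
- 15,000 × 0.008 = 120

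Any elective and emergency mix lies between these. The share that is grade A and closed surgically is not in the documents. As an assumed range only, take 40% to 60% grade A and 10% to 30% of those closed surgically:

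- 60 × 0.4 × 0.1 = 2.4
- 120 × 0.6 × 0.3 = 21.6

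**5. Direction of any distortion.** Assume a 30% complication rate after true common bile duct repair. Let a share f of the records coded that way be minor closures with complication rate m. The observed rate is (1 − f) × 0.30 + f × m.

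| f | m = 5% | m = 15% | m = 30% | m = 40% |
|---|---|---|---|---|
| 10% | 27.5% | 28.5% | 30.0% | 31.0% |
| 25% | 23.75% | 26.25% | 30.0% | 32.5% |
| 50% | 17.5% | 22.5% | 30.0% | 35.0% |

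The observed rate can fall, stay the same or rise, depending on f and m. The documents give neither.

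**The case against.** The strongest reply has four parts.

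- **Detectability.** Strasberg grade is recorded for each injury, so a grade A record with a common bile duct repair can be spotted and set apart. This stands, but only in part. It shows that the code is suspect, not what was done, and it cannot tell a true washout from a closure entered as one.
- **No stated analysis suffers.** The secondary endpoints do not include outcome by repair method, and the prespecified subgroups are operative approach and urgency. This stands. What is harmed is the description of management, not a planned comparison.
- **Few records.** This stands too, and it limits the importance of the point.
- **Definition.** The lead sentence in Appendix D refers to the main biliary tree, so one might argue that grade A is outside it. This does not stand. The list under that sentence starts with grade A, and both the form and the dictionary offer it.

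A reader might infer that minor closures must be coded as common bile duct repairs and so make those repairs look safer. The documents do not support that. Nothing tells collectors to use such a code. The completeness rules (no more than 10% missing per centre, over 95% of data points per record for authorship) discourage blanks but do not direct that choice. A lower apparent complication rate would also require minor closures to have fewer complications, which the documents do not show. Nor does coding as washout only drop all one-year complications, because Section 6 is not conditional on repair.

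**Conclusion.** The gap is real and narrow. An injury that the study itself defines can receive a surgical treatment that the form cannot record accurately, and the case report form and data dictionary share the fault. Those repairs will be missing or misclassified in the management data for secondary aim 2.

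Only the 60 to 120 injuries rest on protocol figures, and they depend on the anticipated sample and the quoted rates holding. The number without a valid code is an unknown fraction of these; the range of about 2 to 22 rests wholly on assumed shares. No direction of bias in complication rates by method is established. The primary endpoint analysis is not shown to be affected. This is a minor point, worth acting on because the correction is cheap.

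**What to change.** In Method of repair, in both Section 4 of the case report form and Appendix B bile duct injury item 8, add two options: *closure of cystic duct, liver-bed or other minor/aberrant duct* and *other (specify)*. Report repair method cross-tabulated by Strasberg grade.

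If records have already been collected, query those graded A to C and marked as surgical repair or washout only, using the patient lists that sites hold for follow-up. This has to happen before the REDCap record ID is stripped at anonymisation, since the protocol describes that ID as the only link to those lists.

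The cost is two extra tick options on a section completed for few patients, plus a matching edit in the translated forms. A retrospective query would reach at most about 120 records at the protocol's own rates. Neither change touches patient care.
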